1.0 INTRODUCTION

1.1 Purpose of this Study:

We are proposing a prospective, randomized, double blinded, placebo-controlled single center study evaluating the role of co-administration of oral sodium chloride with intravenous diuretics in patients hospitalized with acute decompensated heart failure. We are approaching this study with the hypothesis that the use of oral sodium chloride leads to improved effective diuresis (as measured by weight loss) and renal function as compared to placebo in patients hospitalized with acute decompensated heart failure undergoing aggressive intravenous diuretic therapy.

Primary endpoint:

[figure not shown]
Our primary outcome will be a composite outcome of change in weight and change in creatinine from baseline to 96 hours (or discharge) after initiation of sodium chloride capsule administration vs placebo (as analyzed by intention to treat)

The bivariate outcome will be displayed on a two-dimensional grid with individual data points for each patient representing paired changes in both creatinine and weight at 96 hours after randomization (or at discharge) (Fig. 1). A confidence region for the average difference between treatment arms in this bivariate response will be described as an ellipse, and the two treatment arms will be compared with the use of the Hotelling T-square test, which is a multivariate analog of the 2-sample t test used with a single continuous variable.

The null hypothesis is that there is no difference between the treatment groups in this 2-dimensional end point.

Secondary endpoints:

- Change in creatinine [timepoint: enrollment to 96 hours (or discharge)],
- Change in weight [timepoint: enrollment to 96 hours (or discharge)]
- Change in daily urine output [timepoint: day of enrollment, active treatment days 1, 2, 3, 4],
- Change in serum sodium [timepoint: day of enrollment, active treatment days 1, 2, 3, 4],
- Change in thirst distress survey [timepoint: enrollment to 96 hours (or discharge), followup phone call],
- Time to discontinuation of intravenous diuretic therapy [timepoint: enrollment to discharge]
- Total diuretic dosage in oral furosemide equivalents [timepoint: enrollment to 96 hours (or discharge)],
- Daily urine output/daily total furosemide dose [timepoint: day of enrollment, active treatment days 1, 2, 3, 4]
- Guideline directed medical therapy [timepoint: enrollment to discharge]

- Total potassium supplementation required [timepoint: enrollment to 96 hours or discharge]
- Length of index hospitalization [timepoint: enrollment to discharge]
- Heart failure rehospitalizations, unscheduled clinic and emergency department visits [timepoint: discharge to 30 days post discharge]
- Death from any cause [timepoint: enrollment to 90 days post enrollment]
- Initiation of renal replacement therapy or ultrafiltration [timepoint: enrollment to 90 days post enrollment]
- Occurrence of a serious adverse event [timepoint: enrollment to 90 days post enrollment]

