3.0 Study Procedures

Prior to the initiation of participation, a signed and dated informed consent and permission to use protected health information must be obtained. Randomization will occur via REDCAP Randomization Tool

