4.1 Study Evaluations

All study evaluations will be as per clinical standard of care. Research procedures will include the randomization of sodium chloride vs placebo as well as adverse event reporting.

Study Procedures	Time Point 1 Screening/ Enrollment	Time Point 2 Salt vs Placebo Day 1	Time Point 3 Salt vs Placebo Day 2	Time Point 4 Salt vs Placebo Day 3	Time Point 5 Salt vs Placebo Day 4	Time Point 6 Active Treatment Completion Day 5	Time Point 7 Discharge	Time Point 8 Outpatient followup (routine)	Timepoint 9 Followup Phonecall
Informed Consent and Randomization	x								
Collection of baseline characteristics from medical	x								

record (prior medications, PMH, demographics, EF, baseline /admission labs)									
Administer Thirst Distress Survey	x					x			
Vitals and 24 Hour Fluid Balance (Intake/Output)	x	x	x	x	x	x	x	x	
Administration of Salt vs Placebo (2g TID w/ meals)		x	x	x	x				
Collection of Urine electrolytes		x	x	x	x	x	x		
BMP/NT-ProBNP (per usual clinical care)	x	x	x	x	x	x	x	x	
Review of Current Medications and Diet Order	x	x	x	x	x	x	x	x	
Blood draw for biomarker analysis*		x				x			
Adverse Events		x	x	x	x	x	x	x	x
Reason for discontinuation of study drug			x	x	x	x			
Length of hospital stay							x		
Phone Contact Readmission?									x

* Blood draws for biomarker analysis will be limited to the first 50 patients enrolled.

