5.0 Statistical Analysis and Endpoints

5.1 Sample Size and Primary Endpoint:

Population: Acutely decompensated heart failure patients with or at risk for diuretic resistance or congestive nephropathy.

Hypothesis: Use of oral sodium chloride will lead to increased fluid volume removal and attenuate diuretic related renal dysfunction.

Study Design: Prospective, randomized, double blind, placebo controlled, single-center study

Endpoint: Net change in weight and change in creatinine from baseline to 96 hours after initiation of sodium chloride capsule supplementation [or discharge] vs placebo (as analyzed by intention to treat)

Power: 80% (2-sided alpha 0.05)

Sample Size Estimate: 85

Trial	Endpoint	SD	alpha	Power	Difference	Sample size
UNLOAD	Wt change (kg)	3.5	0.5	80	2.2	80
DOSE	Wt change (kg)	4	0.5	80	2.2	104
CARESS-HF	Wt change (kg)	5.1	0.5	80	2.2	168
ATHENA-HF	Wt change (kg)	3.4	0.5	80	2.2	74
Aliti	Wt change (kg)	2.85	0.5	80	2.2	52
3T	Wt change (kg)	2.7	0.5	80	2.2	48
AVERAGE		3.77	0.5	80	2.2	84
<hr/>						
UNLOAD	Cr change (mg/dl)	0.6	0.5	80	0.3	126
CARESS-HF	Cr change (mg/dl)	0.53	0.5	80	0.3	98
Athena-HF	Cr change (mg/dl)	0.3	0.5	80	0.3	32
AVERAGE		0.476	0.5	80	0.3	80

Based on data from the above clinical trials which evaluated diuretic strategies in decompensated heart failure, we believe that 85 patients will give us 80% power to detect a 2.2 kg (5 lb) difference in weight and a 0.3mg/dl difference in serum creatinine levels at 96 hours.

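### The primary Hotelling T-square test on change scores uses no baseline covariates; a prespecified bivariate model with baseline weight and creatinine would be modestly more precise if change depends on baseline

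*Combined protocol and SAP*

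**What the plan says.** Section 1.1 (Primary endpoint) defines a "composite outcome of change in weight and change in creatinine from baseline to 96 hours (or discharge"), to be plotted as one point per patient. The average difference between arms is to be shown with an elliptical confidence region. For the test itself, the plan states: "the two treatment arms will be compared with the use of the Hotelling T-square test, which is a multivariate analog of the 2-sample t test". Section 5.1 repeats the endpoint as "Net change in weight and change in creatinine from baseline to 96 hours". Section 5.4, the analytical plan, consists only of a reference back to the earlier text.

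On allocation, Section 3.0 says "Randomization will occur via REDCAP Randomization Tool" and gives neither a ratio nor a stratification factor. The Section 4.1 schedule has baseline characteristics, including baseline or admission laboratory values, collected at enrollment. No covariate, adjusted model or sensitivity analysis for the primary endpoint appears anywhere in the document.

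**The concern.** A change score subtracts the baseline with a fixed slope of 1. If the regression of the 96-hour value on baseline has a different slope, change still depends on baseline. That dependence then stays in the error term, and through chance imbalance it also enters the estimated difference between arms. A linear model with the baselines as covariates removes it.

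There are about 42 patients per arm and no named stratification. A wider ellipse than necessary matters most if sodium chloride moves only one of the two components, because the two-degree-of-freedom test then has less than 80% power. Also, with no covariates named in advance, any adjustment made after seeing the baseline table would be post hoc.

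**Working it through.** **Inputs from Section 5.1.** "Power: 80% (2-sided alpha 0.05"); "Sample Size Estimate: 85"; effects of 2.2 kg and 0.3 mg/dl; printed average SDs of 3.77 kg and 0.476 mg/dl.

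**Assumptions, because the documents are silent.** Allocation is 1:1 (42/43), there is no dropout, the two changes are uncorrelated, and each change correlates (r) only with its own baseline. The range r = 0 to 0.4 is assumed throughout.

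**The plan's own figure.** The total is twice the rounded-up value of 2(1.96 + 0.842)² SD²/Δ², that is, of 15.70 SD²/Δ².
- Creatinine: 15.70 × 0.476²/0.3² = 39.5, rounded up to 40, total 80, as printed.
- Weight, using the mean of the six listed SDs (3.59): 15.70 × 3.59²/2.2² = 41.8, rounded up to 42, total 84, as printed.
- Weight, using the printed average of 3.77: 46.1, rounded up to 47, total 94.

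So 85 reproduces, but from 3.59 rather than 3.77. The table also prints alpha as 0.5 where its rows need 0.05. Both are separate matters; results for both SDs are given below.

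**Power of the planned test.** The noncentrality is λ = (42 × 43/85) d′S⁻¹d = 21.247 d′S⁻¹d, referred to F(2, 82) with critical value 3.108.
- Weight only: 21.247 × (2.2/3.77)² = 7.235
- Creatinine only: 21.247 × (0.3/0.476)² = 8.440
- Both: 7.235 + 8.440 = 15.675

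**Power with both baselines as covariates.** Residual variances are multiplied by (1 − r²). The noncentrality is multiplied by 81/83 for expected covariate imbalance. The reference distribution is F(2, 80), critical value 3.111. Example, weight only at r = 0.4: 7.235 × (81/83)/0.84 = 8.406.

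| Effect present | Unadjusted | r = 0 | r = 0.2 | r = 0.3 | r = 0.4 |
|---|---|---|---|---|---|
| Weight only | 65.4% | 64.2% | 66.1% | 68.6% | 72.3% |
| Creatinine only | 72.5% | 71.4% | 73.2% | 75.7% | 79.1% |
| Both | 94.6% | 94.0% | 94.9% | 95.9% | 97.1% |
| Change in ellipse area | – | +2.6% | −1.5% | −6.6% | −13.8% |

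Break-even is at r = 0.158 for all three patterns: 1 − r² = 0.975 there, which offsets 81/83 = 0.976 and the two lost degrees of freedom.

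**Sensitivity.**
- With a weight SD of 3.59, weight-only power is 69.9% unadjusted and 76.7% adjusted at r = 0.4. The gain is 6.8 points, against 6.9 with 3.77. Power for both effects is 95.5% unadjusted and 97.7% adjusted.
- With r = 0.1 for weight and 0.3 for creatinine, adjusted power is 64.7% (weight only), 75.7% (creatinine only) and 95.2% (both).
- If the two changes correlate at +0.3 and both effects are present, power is 87.3% unadjusted and 86.4 / 87.8 / 89.5 / 91.9% adjusted at r = 0 / 0.2 / 0.3 / 0.4. At −0.3 it is 99.0% unadjusted and 98.9% to 99.7% adjusted.
- Simulation with 20,000 trials per cell agreed. Type I error was 5.1–5.2% unadjusted and 4.8–5.2% adjusted. At r = 0.4, adjusted power was 72.4%, 79.2% and 97.1%.

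**Chance imbalance.** The standard error of a baseline difference is √(1/42 + 1/43) = 0.217 SD. A 1.96-standard-error imbalance shifts the unadjusted estimate by r × SD × 1.96 × 0.217. For r = 0.2 to 0.4 this is 0.32 to 0.64 kg and 0.04 to 0.08 mg/dl. It is the same variance seen another way, not an additional loss.

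**The case against.** The strongest reply is that nothing is wrong. The unadjusted test is valid, Section 1.1 fixes the endpoint, test, region and null hypothesis, and the change score already takes out much of the baseline variation. The documents give no r, so they do not show that adjustment helps. Below about 0.16 it costs a little, and at 0.2 the gain is under one point. Section 5.1 plans for "80% power to detect a 2.2 kg (5 lb) difference in weight and a 0.3mg/dl difference in serum creatinine levels at 96 hours"; with both effects and uncorrelated changes, adjustment moves power by only −0.6 to +2.5 points over r = 0 to 0.4. Because one unadjusted test is already prespecified, baseline imbalance forces no later choice. An ellipse of adjusted differences would not correspond exactly to the raw points on the grid. A linear baseline term also gives leverage to a few high creatinine values, since eligibility excludes only an eGFR below 15.

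Most of this stands as a limit on the claim: the test is valid, r is unknown, and the gain is small when both components respond. It does not remove the point. The trade is uneven: at most about 1.2 points lost at r = 0, against about 7 gained at r = 0.4 when one component responds. The display and leverage worries are minor if the raw grid and the unadjusted test are both kept. The post hoc argument is a supporting reason only.

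**Conclusion.** The concern holds as a worthwhile improvement, not as an error. The primary test uses no baseline covariates although both are available. Adjustment would add up to about 7 points of power if only one component responds and r is 0.4, and up to 2.5 points if both respond and the changes are uncorrelated. It would cost at most about 1.2 points if change is unrelated to baseline. These figures rest on the assumed r, 1:1 allocation, no dropout and the Section 5.1 SDs. The choice between 3.77 and 3.59 kg alters the level of power but hardly the gain. Adjustment does not by itself secure 80% power for a single-component effect: at r = 0.4 with the printed SDs it reaches 72.3% and 79.1%.

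**What to change.** In Sections 1.1 and 5.4, replace the primary test with text along these lines:

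> The primary comparison is the two-degree-of-freedom test of treatment (Hotelling–Lawley) from a bivariate linear model of weight change and creatinine change on arm, baseline weight and baseline creatinine. The confidence ellipse is drawn from the adjusted differences. The unadjusted Hotelling T-square test is reported as a sensitivity analysis.

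Keep the grid of individual raw changes, and label the ellipse as adjusted. Use the same covariates for the two single-component secondary endpoints, change in creatinine and change in weight.

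The cost is one or two sentences and two degrees of freedom, with no new data or patients. The change should be made before any unblinded data are seen. If r proves to be zero, power falls from 65.4% to 64.2%, from 72.5% to 71.4%, or from 94.6% to 94.0%, depending on which effects are present.

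### The 80% power in section 5.1 is not the power of the primary Hotelling T-square test, and its average weight SD does not give the printed sample size

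*Combined protocol and SAP*

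**What the plan says.** The primary outcome in section 1.1 is the pair of changes in weight and creatinine from baseline to 96 hours or discharge, and "the two treatment arms will be compared with the use of the Hotelling T-square test". The display is a patient-level grid, and "A confidence region for the average difference between treatment arms in this bivariate response will be described as an ellipse". The null is stated as: "The null hypothesis is that there is no difference between the treatment groups in this 2-dimensional end point". Each component is also a separate secondary endpoint, for example "Change in weight [timepoint: enrollment to 96 hours (or discharge)".

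The study hypothesis is directional on both components. Section 1.1 expects "improved effective diuresis (as measured by weight loss) and renal function as compared to placebo", and section 5.1 says "Use of oral sodium chloride will lead to increased fluid volume removal and attenuate diuretic related renal dysfunction".

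Section 5.1 gives "Power: 80% (2-sided alpha 0.05)", a sample size estimate of 85, and a table with six weight rows and three creatinine rows. Each row has one SD, one difference and one N. The average rows print SD 3.77 kg with N 84 for weight, and SD 0.476 mg/dl with N 80 for creatinine. The text concludes that "85 patients will give us 80% power to detect a 2.2 kg (5 lb) difference in weight" and a 0.3 mg/dl difference in creatinine. No correlation between the two changes and no T-square calculation appears. Section 5.4 only refers back to the earlier text.

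**The concern.** There are two planning problems and one lesser point of interpretation.

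- **Power of the wrong test.** The 80% is attached to the trial as a whole, but it is worked out for weight alone and creatinine alone. T-square power depends on both standardised effects and on the within-arm correlation between them. A reader cannot learn from section 5.1 what chance the primary analysis has of succeeding.
- **A wrong input.** The average weight row does not agree with itself: its SD does not lead to its N. Anyone checking or reusing the calculation cannot tell which of the two was intended.
- **Direction (lesser).** The T-square test rejects for a difference in any direction, including one component better and the other worse. The hypothesis requires benefit on both. The plan does not say in words how a significant p-value relates to that two-part claim.

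**Working it through.** **Inputs from section 5.1:** differences 2.2 kg and 0.3 mg/dl; SDs as listed; two-sided alpha 0.05; N = 85. The table's alpha column prints 0.5, but its rows reproduce only at the 0.05 given in the text. **Assumptions, because the documents are silent:** 1:1 allocation (42/43), and within-arm correlation rho from -0.5 to +0.5, with both components coded so that positive means benefit.

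**1. Reproducing the table.** n per arm = 2 × ((1.960 + 0.842) × SD / difference)², rounded to the nearest integer and doubled.

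- Weight SDs 3.5, 4, 5.1, 3.4, 2.85, 2.7 give 80, 104, 168, 74, 52, 48. All six match.
- Creatinine SDs 0.6, 0.53, 0.3 give 126, 98, 32. All three match.
- Creatinine average, 0.476: 39.5 per arm, so 80. This matches.
- Weight average, 3.77: 46.1 per arm, so 92 (94 if rounded up). The table prints 84.

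The formula is the two-sample comparison of one mean, so the 80% is single-endpoint power.

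**2. Source of the mismatch.** (3.5 + 4 + 5.1 + 3.4 + 2.85) / 5 = 3.77, which leaves out the sixth row. Adding 2.7 and dividing by 6 gives 21.55 / 6 = 3.59, hence 41.8 per arm and a total of 84. The printed N agrees with all six rows; the printed SD does not.

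**3. Single-endpoint power at N = 85 (t test).** Weight: 76% with SD 3.77, 80% with SD 3.59. Creatinine: 82%.

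**4. T-square power at N = 85.** Noncentral F(2, 82), with noncentrality λ = (42 × 43 / 85) × (a² + b² − 2·rho·a·b) / (1 − rho²). Here a = 2.2/3.77 = 0.584 or 2.2/3.59 = 0.613, b = 0.3/0.476 = 0.630, and 42 × 43 / 85 = 21.25. At rho 0 and SD 3.77, λ = 21.25 × (0.341 + 0.397) = 15.7, which gives 95%.

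| True effect | rho -0.5 | rho 0 | rho +0.5 |
|---|---|---|---|
| Both as planned | over 99% | 95% | 82-84% |
| Weight only | 78-83% | 65-70% | 78-83% |
| Creatinine only | 85% | 73% | 85% |

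Ranges run from SD 3.77 to SD 3.59. With both effects as planned, power falls below 80% only when rho exceeds about 0.57-0.64.

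**5. Direction.** These are shares of all trials, from 400,000 simulated trials per setting over the same rho and SD ranges.

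- Both effects as planned: significant with the two estimates of opposite sign in 0.1-0.5%.
- Weight at half its planned effect (1.1 kg), creatinine as planned: 4-9%.
- Only one component truly improves: 32-42%, about half of the significant results. By symmetry, the estimate of a null component has the wrong sign half the time.
- Same one-component case, counting only trials in which the other component is nominally significantly worse (two-sided p < 0.05): about 2.5%.

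**The case against.** **On power and the SD.** The table labels each row as weight or creatinine, so its single-endpoint basis is visible. The printed 84 follows from the six listed rows, so the SD is a clerical slip and N need not change. With both planned effects, T-square power is at least 82% over the range of rho shown. All of this stands, and it rules out a reading that a reader might infer: that 85 patients are too few for the primary test. The documents do not support that for the planned alternative. What remains is that the SD is wrong as printed and the power sentence does not describe the analysis it is meant to justify.

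**On direction.** The hypothesis is already an *and* claim, so a result better on one component and worse on the other fails it on a plain reading. The ellipse and the two component secondary endpoints would show the signs. That also stands. Two stronger readings are tempting:

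- *The plan would let a trade-off count as success.* No passage says so, and the wording of the hypothesis points the other way. Fig. 1 is not shown, so the absence of a rule rests on the text alone.
- *Half of all significant results would be contradictory.* That holds only if one component has no true effect, and it counts every wrong sign, however small. A nominally significant opposite effect is far rarer, at about 2.5%.

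Nor is a success rule based on the signs of the two estimates clearly the remedy. When only one component improves, it would still read the trial as supporting in 33-42%.

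**Conclusion.** The concern holds mainly as a fault in the power justification. The average weight SD is wrong as printed, and the 80% belongs to single-endpoint comparisons. If 3.77 kg really is the planning value, power for weight alone is 4 points below the stated 80%. If 3.59 is, the table is coherent. In either case T-square power is adequate when both effects occur, and below 80% at rho 0 when only one does. These T-square figures rest on 1:1 allocation, approximate normality, the SDs in section 5.1 and an assumed range for rho.

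The direction point is real but secondary. It matters little under the planned effects and calls for a clarifying statement, not a new test or a formal success rule.

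**What to change.** Keep N at 85.

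1. **Section 5.1, table.** Change the average weight SD to 3.59. If 3.77 is intended, restate the weight power at N = 85 as about 76%.
2. **Section 5.1, power statement.** Label the 80% as single-endpoint power. Add T-square power at N = 85 for 2.2 kg and 0.3 mg/dl over a stated range of within-arm correlation, for example -0.5 to +0.5, with the sign coding given.
3. **Section 1.1, primary endpoint.** Add: *A significant Hotelling T-square result does not by itself establish the study hypothesis. Both between-arm differences will be reported with 95% confidence intervals beside the primary p-value and ellipse. Differences of opposite sign will be described as not supporting the two-part hypothesis.*

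The cost is a few sentences, one table cell and one power calculation, with no extra patients or data. The drawback is that some restated power figures fall below 80%. Requiring each component to be individually significant is not proposed: at rho 0 its power would be only 62-65% (0.76 × 0.82 to 0.80 × 0.82, before rounding).

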1.2 Importance and Rationale of Study

Dietary sodium restriction is a common therapeutic intervention in the management of patients hospitalized with decompensated heart failure. This is despite limited supportive data and inconsistent society guidelines.¹⁻³ Randomized clinical trial data has shown that dietary sodium restriction in patients hospitalized with heart failure was not associated with differences in weight, clinical congestion, time to clinical stability but was associated with increased thirst.⁴ Numerous studies demonstrate that sodium restriction is associated with increased renin-angiotensin-aldosterone system activation as well as increases in inflammatory markers.^{5,6} These findings challenge of the role of sodium restriction in hospital management of heart failure and have lead to trials that consider a therapeutic role of providing sodium to patients with acute heart failure for its effect in attenuating neurohormonal activation during aggressive diuresis. A central example is the SMAC-HF study from Italy, which showed that in 1771 patients with acute NYHA class IV heart failure, the addition of hypertonic saline (150ml of 1.4%-4.6% NaCl twice a day in addition to diet liberalization led to statistically significant increased urine output and weight loss in addition to reductions in creatinine, length of stay, mortality and readmissions.⁷ These findings are controversial but similarly favorable results with the use of hypertonic saline in aiding diuresis have been seen in Japan with improved diuresis with continuous hypertonic saline infusions.⁸ Despite these results, use of sodium chloride supplementation in acute heart failure remains limited. This may be because the practice challenges ingrained clinical practice, but a more likely reason is that the manner of sodium chloride delivery in these trials (hypertonic saline) is often reserved for the ICU setting and central venous access for delivery. While small volumes of hypertonic saline are likely safe to be administered in a non-ICU setting, the results would be more broadly applicable and utilized if the manner of sodium supplementation did not require intensive monitoring or central venous access, ie oral supplementation. Therefore, the purpose of the **“Oral Sodium to Preserve Renal Efficiency in Acute Heart Failure”** (OSPREY-AHF) is to evaluate the efficacy and safety of oral sodium chloride supplementation compared to placebo in patients with acute decompensated heart failure. While we are specifically interested in sodium chloride and its hypothesized role in attenuating a neurohormonally mediated diuretic resistance commonly seen in patients requiring high dose diuretic therapy, we also intend that by focusing on oral sodium chloride supplementation we may clarify the role of dietary sodium restriction in hospitalized patients with acute heart failure.
